9.1 ADVERSE EVENTS AND SERIOUS ADVERSE EVENTS

9.1.1 DEFINITION OF ADVERSE EVENTS (AE)

Adverse event means any untoward medical occurrence associated with the use of an intervention in humans, whether or not considered intervention-related (21 CFR 312.32 (a)).

9.1.2 DEFINITION OF SERIOUS ADVERSE EVENTS (SAE)

An adverse event (AE) or suspected adverse reaction is considered "serious" if, in the view of either the investigator or sponsor, it results in any of the following outcomes: death, a life-threatening adverse event, inpatient hospitalization or prolongation of existing hospitalization, a persistent or significant incapacity or substantial disruption of the ability to conduct normal life functions, or a congenital anomaly/birth defect. Important medical events that may not result in death, be life-threatening, or require hospitalization may be considered serious when, based upon appropriate medical judgment, they may jeopardize the participant and may require medical or surgical intervention to prevent one of the outcomes listed in this definition.

9.1.3 CLASSIFICATION OF AN ADVERSE EVENT

9.1.3.1 SEVERITY OF EVENT

Adverse event severity will be graded as follows:

- **Mild** – Events require minimal or no treatment and do not interfere with the participant's daily activities.
- **Moderate** – Events result in a low level of inconvenience or concern with the therapeutic measures. Moderate events may cause some interference with functioning.
- **Severe** – Events interrupt a participant's usual daily activity and may require systemic drug therapy or other treatment. Severe events are usually potentially life-threatening or incapacitating. Of note, the term "severe" does not necessarily equate to "serious".

9.1.3.2 RELATIONSHIP TO STUDY INTERVENTION

All adverse events (AEs) will have their relationship to study intervention assessed by the clinician who examines and evaluates the participant based on temporal relationship and his/her clinical judgment. The degree of certainty about causality will be graded using the categories below. In a clinical trial, the study product must always be suspect.

- **Definitely Related** – There is clear evidence to suggest a causal relationship, and other possible contributing factors can be ruled out. The clinical event, including an abnormal laboratory test result, occurs in a plausible time relationship to study intervention administration and cannot be explained by concurrent disease or other drugs or chemicals. The response to withdrawal of the study intervention (de-challenge) should be clinically plausible. The event must be pharmacologically or phenomenologically definitive, with use of a satisfactory re-challenge procedure if necessary.
- **Probably Related** – There is evidence to suggest a causal relationship, and the influence of other factors is unlikely. The clinical event, including an abnormal laboratory test result, occurs within a reasonable time after administration of the study intervention, is unlikely to be attributed to concurrent disease or other drugs or chemicals, and follows a clinically reasonable response on withdrawal (de-challenge). Re-challenge information is not required to fulfill this definition.
- **Potentially Related** – There is some evidence to suggest a causal relationship (e.g., the event occurred within a reasonable time after administration of the trial medication). However, other factors may have contributed to the event (e.g., the participant's clinical condition, other concomitant events). Although an AE may rate only as "possibly related" soon after discovery, it

can be flagged as requiring more information and later be upgraded to “probably related” or “definitely related”, as appropriate.

- **Unlikely to be related** – A clinical event, including an abnormal laboratory test result, whose temporal relationship to study intervention administration makes a causal relationship improbable (e.g., the event did not occur within a reasonable time after administration of the study intervention) and in which other drugs or chemicals or underlying disease provides plausible explanations (e.g., the participant’s clinical condition, other concomitant treatments).
- **Not Related** – The AE is completely independent of study intervention administration, and/or evidence exists that the event is definitely related to another etiology. There must be an alternative, definitive etiology documented by the clinician.

9.1.3.3 EXPECTEDNESS

The PI and medical investigator will be responsible for determining whether an adverse event (AE) is expected or unexpected. An AE will be considered unexpected if the nature, severity, or frequency of the event is not consistent with the risk information previously described for the study intervention as reported in the IB.

9.1.4 TIME PERIOD AND FREQUENCY FOR EVENT ASSESSMENT AND FOLLOW-UP

The occurrence of an adverse event (AE) or serious adverse event (SAE) may come to the attention of study personnel during study visits, and interviews of a study participant presenting for medical care, or upon review by a study monitor.

All AEs including local and systemic reactions not meeting the criteria for SAEs will be captured on the appropriate case report form (CRF). Information to be collected includes event description, time of onset, clinician’s assessment of severity, relationship to study product (assessed only by those with the training and authority to make a diagnosis), and time of resolution/stabilization of the event. All AEs occurring after signing the informed consent must be documented appropriately regardless of relationship. All AEs will be followed to adequate resolution.

Changes in the severity of an AE will be documented to allow an assessment of the duration of the event at each level of severity to be performed. AEs characterized as intermittent require documentation of onset and duration of each episode.

A study team member will record all reportable events with start dates occurring any time after informed consent is obtained until 7 days after the last day of administration of the medication. At each study visit, a research team member will be responsible for notifying the Food and Drug Administration (FDA) of any unexpected fatal or life-threatening suspected adverse reaction as soon as possible, but in no case later than 7 calendar days after the initial acquisition of the information.

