MBX-2982 was not genotoxic in any of the systems evaluated, but no data are available regarding animal or human carcinogenicity. No specific animal or human studies have been performed to determine the reproductive and developmental toxicity of MBX-2982. In human studies to date, there have been no reported cases of pregnancy in subjects receiving MBX-2982 or in partners of subjects receiving MBX-2982. There is no information about the effect of MBX-2982 on sperm or its production in the body, nor is there information about effects on the development of the fetus.

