2.3.3.2 MITIGATION OF POTENTIAL RISKS ASSOCIATED WITH THE INVESTIGATIONAL DRUG

The drug was well tolerated and had a very low order of toxicity at the proposed concentration in previous human studies and at higher concentrations in animal models.

It is important that women of childbearing potential receiving MBX-2982 in early investigational development do not become pregnant for at least 2 weeks after the last dose. As a precaution, women of childbearing potential receiving MBX-2982 should use at least one medically accepted method of contraception with >99% effectiveness when used consistently and correctly. As the induction potential of MBX-2982 on CYP enzymes is not clear. Given that the effectiveness of hormonal contraceptives can be reduced by CYP enzyme inducers, we recommend that study subjects who are women of childbearing potential use a barrier method during the study to prevent unintended pregnancy. In addition, it is important that partners of male subjects receiving MBX-2982 should not become pregnant during the study. As a precaution, male subjects receiving MBX-2982 should use dual method of contraceptive use: medically accepted contraception (e.g., condoms w/spermicide), or their partner should also use a medically accepted form of contraception along with condoms during this period.

Although the studies in humans did not show clinically relevant ECG alterations, in vitro studies showed potential for QT prolongation. For this reason, ECGs will be performed on Visits 4, 5, 7, 8 during investigational medication treatment, in addition to the screening Visit 1. At visits 5 and 8, the ECG will be performed during the meal test at the time of predicted drug concentration peak 180 min after taking the medication. The QTcF will be manually calculated for each ECG.

Elevated TSH levels were reported in one of the human studies but not confirmed in others. TSH and FT4 have been added to the safety measures at visit 5 and visit 8 during study treatment.

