4.4 END OF STUDY DEFINITION

A participant is considered to have completed the study if he or she has completed all phases of the study including the end of trial visit seven days after the last dose of the study medication as shown in the Schedule of Activities (SoA).

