5 STUDY POPULATION

5.1 INCLUSION CRITERIA

Type 1 diabetes cohort

1. Age 20-60 years
2. Diagnosis of T1DM according to American Diabetes Association (ADA) criteria continuously requiring insulin for survival
3. Diabetes diagnosis performed more than 5 years before enrollment
4. Fasting C-peptide levels < 0.7 ng/mL with a concurrent plasma glucose concentration > 90 mg/dL (Labs may need to be repeated if the Plasma glucose is \leq 90 mg/dL)
5. For female participants: must be > 6 months post-partum and not lactating and agrees not to become pregnant during the study and for at least 2 weeks after the last dose of the study medication. For male participants: agrees not to donate sperm or not to get a woman pregnant during the study and for at least 2 weeks after the last dose of the study medication.

Healthy subject cohort

1. Age 20-60 years
2. General good health
3. Creatinine clearance >80 mL/min based on CKD-EPI equation
4. Fasting blood glucose (FBG) >70 mg/dL and <100 mg/dL
5. No history of diabetes
6. For female participants: must be > 6 months post-partum and not lactating and agrees not to become pregnant during the study

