9.1.7 REPORTING OF PREGNANCY

Pregnancy in a study participant will be reported among adverse events and reported to the IRB and regulatory agencies.

The study medication will be discontinued, and no additional study tests will be done, while continuing safety follow up.

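### Pregnancy collection stops short of the protocol's own two-week precaution after the last dose: events are recorded to 7 days, no test follows Visit 8, and section 9.1.7 omits partners

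*Combined protocol and SAP*

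**What the plan says.** **The precaution.** Section 5.1 requires that a woman with type 1 diabetes "agrees not to become pregnant during the study and for at least 2 weeks after the last dose of the study medication", and that a man "agrees not to donate sperm or not to get a woman pregnant during the study and for at least 2 weeks". Section 2.3.3.2 repeats the period for women, who are to "do not become pregnant for at least 2 weeks after the last dose". It adds that "it is important that partners of male subjects receiving MBX-2982 should not become pregnant during the study". The reason is in section 2.3.1.2: there are no reproductive or developmental toxicity studies, and "There is no information about the effect of MBX-2982 on sperm or its production in the body".

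**The recording period.** Section 9.1.4 takes reportable events with start dates from consent "until 7 days after the last day of administration of the medication". Section 4.4 places "the end of trial visit seven days after the last dose of the study medication". The Schedule of Activities and section 8.1.11 put that visit at Day 49±2.

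**The tests.** The Schedule of Activities lists urine pregnancy tests at Visits 3, 5, 6 and 8. Visit 9 has a blood count and metabolic panel, and no pregnancy test.

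**The reporting rule.** Section 9.1.7 says: "Pregnancy in a study participant will be reported among adverse events and reported to the IRB and regulatory agencies". It gives no period of its own and does not mention partners. Section 9.2.2 gives a route by which the second site notifies the coordinating site of pregnancy events, again with no period and no mention of partners.

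**The concern.** The two-week precaution is the protocol's own statement of how long after dosing a conception should be treated as a possible drug exposure. The arrangements for finding and recording such a conception are shorter. Section 9.1.7 places pregnancy among adverse events, so the 7-day limit in section 9.1.4 can be read as applying to it. No visit, call or test is scheduled after Visit 9.

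The safety record is what is at stake. Section 2.3.1.2 reports that earlier human studies saw no pregnancies in subjects or in their partners. This trial could not update that statement reliably: a participant's pregnancy might surface after the last contact, and the operative safety sections do not ask for a partner's pregnancy at any time.

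**Working it through.** **Inputs.** Last dose: morning of the clamp day, nominally Day 42 (8.1.10, 8.2). Visit 8 window: +5 days. Visit 9: Day 49±2. Precaution: at least 14 days after the last dose (5.1). Recording: 7 days after the last dose (9.1.4).

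**1. The plan's own figures.** Visit 9 minus last dose = 49 − 42 = 7 days, which agrees with section 4.4. Day −35 to Day 49 = 84 days, which agrees with the stated enrollment.

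**2. Nominal gap.** The precaution ends on Day 42 + 14 = Day 56. Recording ends on Day 42 + 7 = Day 49. Uncovered: 56 − 49 = 7 of 14 days.

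**3. With the visit windows.** The last dose falls on Day 42 to 47 and Visit 9 on Day 47 to 51.

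| Quantity | Nominal | Range |
|---|---|---|
| Recording ends (last dose + 7) | Day 49 | Day 49 to 54 |
| Precaution ends (last dose + 14) | Day 56 | Day 56 to 61 |
| Visit 9 minus last dose | 7 days | 47 − 47 = 0 to 51 − 42 = 9 days |
| Precaution days left after Visit 9 | 7 days | 14 − 9 = 5 to 14 − 0 = 14 days |
| Pregnancy tests after Visit 8 | 0 | 0 |

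Visit 9 is tied to a study day and not to the actual last dose. After a delayed clamp it can therefore fall fewer than 7 days after dosing, which does not agree with section 4.4.

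**4. Which sequence is affected.** In active-then-placebo, the last active dose is on Day 14 to 19, so the 14 days after active drug end on Day 28 to 33. Visit 8 starts on Day 41 at the earliest, 41 − 33 = 8 or more days later, and includes a test. That sequence is covered after active drug as far as women are concerned. The gap after active drug lies in placebo-then-active, which under 1:1 allocation is 10 of the 20 participants. Within it, the gap concerns women of childbearing potential and the partners of men; the documents give neither number.

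**5. Expected size.** Two assumptions are needed: a 1% annual failure rate (reading the 99% effectiveness in section 5.2 as an annual figure), and 5 to 10 people at risk in that sequence. Expected conceptions in the two post-dose weeks = n × 0.01 × 2/52:
- n = 5: 0.002
- n = 10: 0.004

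Adding the two weeks of Period 2 dosing doubles these to about 0.004 and 0.008.

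**The case against.** The strongest reply is that the documents do not contradict themselves. One passage sets a rule of behavior and another sets a recording period, and nothing promises surveillance for 14 days. That is correct, and the point is a mismatch of design, not an inconsistency. The Visit 9 timing against section 4.4 is the only part that needs reconciling as such.

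A reader might infer that affected conceptions would certainly go undetected and unreported. The documents do not support that. A conception late in Period 2 has a start date inside the 7-day limit. Section 9.1.7 sets no limit of its own, and the adverse event review at Visit 9 may bring out a pregnancy the participant already knows about. What is missing is an active step to find one and a clear rule for later ones. The instruction to follow adverse events to resolution does not fill this, since it concerns events already recorded.

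A reader might also infer that the last test is fixed before the final dose. That order is likely, because the test is listed among the procedures ahead of the meal challenge and the final dose is at about 6 a.m. on the second day. But Visit 8 spans two days and the test is not dated within them. It makes little difference: a test on either day cannot detect a conception after the last dose.

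The half-lives in section 2.2.6 are 18.4 to 29.1 (hours assumed). Seven days is then 168/29.1 = 5.8 half-lives at the longest, leaving about 2% of drug. This suggests low exposure in the second week. However, the figures are for the free base, not the salt used here, and the protocol chose two weeks nonetheless.

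Finally, the consent pages were removed from the text available for review and may contain partner wording. The point is therefore limited to the protocol's safety sections.

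**Conclusion.** The concern stands as a modest gap in safety collection. Measured against the protocol's own two-week precaution, 7 of 14 days nominally fall outside event recording, and 5 to 14 days fall after the last visit once the windows are used. No pregnancy test is scheduled after Visit 8, and section 9.1.7 does not reach partners. Conceptions late in Period 2 or in the two weeks after it could be missed.

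It would be wrong to read this as 10 of 20 participants lacking a needed test. Ten is the size of the placebo-then-active sequence, and only an unstated part of it consists of women of childbearing potential. Under the stated assumptions far less than one conception is expected. The primary endpoints and sample size are untouched. The change is worth making because it is cheap and because, without it, the absence of reported pregnancies would say little.

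**What to change.** 1. Add the existing urine point-of-care pregnancy test to Visit 9 in the Schedule of Activities and section 8.1.11. This helps detect conceptions during Period 2. It will not detect those of the preceding days, so it is not enough alone.
2. State in sections 9.1.4 and 9.1.7 that a pregnancy conceived up to the end of the protocol's two-week period is reportable whenever it becomes known. Add one phone contact, with a home test where applicable. Time it far enough beyond the two weeks for a test to be informative about conceptions near their end; a call immediately after Day 14 post-dose would be too early.
3. Extend section 9.1.7 to pregnancies in partners of male participants, with the partner's consent.
4. Reconcile the fixed Day 49±2 for Visit 9 with the seven days after the last dose in section 4.4.

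Because the trial is blinded, one rule for all participants with type 1 diabetes is the practical form. The cost is one urine test per woman of childbearing potential at an existing visit, one short call per participant with type 1 diabetes (20 at most), and protocol and consent wording. The contraception requirement, dosing and analysis do not change.

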9.1.5 REPORTING EVENTS TO PARTICIPANTS

N/A

9.1.6 EVENTS OF SPECIAL INTEREST

High and low glycemic events will be recorded by CGM and through the participant's history and glucose log at each visit. Hypoglycemia will be defined and recorded according to the American Diabetes Association guidelines (Level 1 hypoglycemia is defined as a measurable glucose concentration <70 mg/dL (3.9 mmol/L) but \geq 54 mg/dL (3.0 mmol/L). Level 2 hypoglycemia (defined as a blood glucose concentration <54 mg/dL [3.0 mmol/L]) is the threshold at which neuroglycopenic symptoms begin to occur and requires immediate action to resolve the hypoglycemic event. Level 3 hypoglycemia is defined as a severe event characterized by altered mental and/or physical functioning that requires assistance from another person for recovery. Hypoglycemic events are among the endpoints measured to evaluate the effects of MBX-2982 on patterns of glycemia as described in section 3.

9.1.7 REPORTING OF PREGNANCY

Pregnancy in a study participant will be reported among adverse events and reported to the IRB and regulatory agencies.

The study medication will be discontinued, and no additional study tests will be done, while continuing safety follow up.

9.2 UNANTICIPATED PROBLEMS

9.2.1 DEFINITION OF UNANTICIPATED PROBLEMS (UP)

The Office for Human Research Protections (OHRP) considers unanticipated problems involving risks to participants or others to include, in general, any incident, experience, or outcome that meets all of the following criteria:

- Unexpected in terms of nature, severity, or frequency given (a) the research procedures that are described in the protocol-related documents, such as the Institutional Review Board (IRB)-approved research protocol and informed consent document; and (b) the characteristics of the participant population being studied;
- Related or possibly related to participation in the research ("possibly related" means there is a reasonable possibility that the incident, experience, or outcome may have been caused by the procedures involved in the research); and
- Suggests that the research places participants or others at a greater risk of harm (including physical, psychological, economic, or social harm) than was previously known or recognized.

9.2.2 UNANTICIPATED PROBLEM REPORTING

The investigator will report unanticipated problems (UPs) to the reviewing Institutional Review Board (IRB). The UP report will include the following information:

- Protocol identifying information: protocol title and number, PI's name, and the IRB project number;
- A detailed description of the event, incident, experience, or outcome;
- An explanation of the basis for determining that the event, incident, experience, or outcome represents an UP;

- A description of any changes to the protocol or other corrective actions that have been taken or are proposed in response to the UP.

To satisfy the requirement for prompt reporting, UPs will be reported using the following timeline:

- UPs that are serious adverse events (SAEs) will be reported as described above (see SAE reporting).
- Any other UP will be reported to the IRB within 10 days of the investigator becoming aware of the problem.
- All UPs should be reported to appropriate institutional and regulatory officials (as required by an institution's written reporting procedures), the supporting agency head (or designee), and the Office for Human Research Protections (OHRP) within 10 business days, of the IRB's receipt of the report of the problem from the investigator per the guidelines per AH policy.

The TRI has a standing committee that meets monthly to review all adverse events in our clinical trials and will additionally be charged with review of the study. ProSciento will report adverse events to TRI monthly. SAE/Unanticipated/Pregnancy events will be reported via email/call during working hours. After hours ProSciento will contact our on call line [contact] or [name] via cell.

9.2.3 REPORTING UNANTICIPATED PROBLEMS TO PARTICIPANTS

N/A

10 STATISTICAL CONSIDERATIONS

10.1 STATISTICAL HYPOTHESES

For the primary endpoints, we hypothesize that the medication (14-day administration of MBX-2982) will increase the measured glucose counter-regulation to hypoglycemia expressed as the maximal glucagon concentration, AUC, and Incremental AUC (iAUC) for glucagon during hypoglycemia compared to placebo. For the secondary endpoints, we hypothesize that the medication:

- will increase hepatic glucose production during insulin-induced hypoglycemia and during a subsequent recovery to euglycemia;
- will reduce the time of recovery from hypoglycemia to euglycemia;
- will increase other counter-regulatory hormones;
- the above-mentioned effects will approach the counter-regulatory response in healthy (non-diabetic) volunteers during insulin-induced hypoglycemia;

Exploratory analysis will:

- evaluate for any effects of a GPR119 agonist upon fasting and/or postprandial glucagon concentrations in T1DM, together with potential effects on fasting and postprandial, GLP-1 and GIP;
- collect data patterns of glycemia of participants with T1DM while are receiving daily therapy with a GPR119 agonist (or placebo);
- evaluate the pharmacokinetic profile of MBX-2982 in participants with T1DM.

10.1.1.1 PRIMARY EFFICACY ENDPOINT(S):

- Maximal glucagon concentration during hypoglycemia
- Total area under the curve (AUC) for glucagon during hypoglycemia
- Incremental AUC for glucagon during hypoglycemia above baseline levels during euglycemia

10.1.1.2 SECONDARY EFFICACY ENDPOINT(S):

- HGP during insulin-induced hypoglycemia
- HGP during recovery from insulin-induced hypoglycemia to euglycemia
- Time of recovery from hypoglycemia (time to reach 85 mg/dL)
- Plasma levels of counter regulatory hormones during hypoglycemia: epinephrine, cortisol, GH

10.1.1.3 EXPLORATORY ENDPOINT(S):

- Levels of GLP-1, GIP in fasting and post-prandial conditions
- Continuous glucose monitoring (CGM) indices of glycemic control including hypoglycemia (percent of time < 70 mg/dL, < 54 mg/dL), hypoglycemic events, mean glucose, percent of time 70-180 mg/dL, percent of time > 180 mg/dL, percent of time > 250 mg/dL, glycemic variability.
- MBX-2982 plasma levels

